8.0 PHARMACEUTICAL INFORMATION

8.1 Investigational Agents

8.1.1 Name of Agent: Decitabine

Product description:

Decitabine is manufactured for Otsuka pharmaceuticals and is commercially available. It is supplied as a sterile, lyophilized white to almost white powder, in a single-dose vial, packaged in cartons of 1 vial. Each vial contains 50 mg of decitabine.

Solution preparation:

For Administration Within 15 Minutes of Preparation: If Decitabine is intended to be administered within 15 minutes from the time of preparation, dilute the reconstituted solution with room temperature (20°C - 25°C) 0.9% Sodium Chloride Injection or 5% Dextrose Injection to a volume of 5mL.

For Delayed Administration: If Decitabine is intended to be administered after 15 minutes of preparation, dilute the reconstituted solution with 5mL of cold (2°C - 8°C) 0.9% Sodium Chloride Injection or 5% Dextrose Injection. Store at 2°C - 8°C for up to 4 hours. Diluted stored solution must be used within 4 hours from the time of preparation. Use the diluted, refrigerated solution within 4 hours from the time of preparation or discard. Parenteral drug products should be inspected visually for particulate matter and discoloration prior to administration, whenever solution and container permit. Do not use if there is evidence of particulate matter or discoloration.

Storage requirements:

Store vials at 25°C (77°F); excursions permitted to 15-30°C (59-86°F)

Route of administration:

To provide a homogeneous suspension, the contents of the syringe must be re-suspended by inverting the syringe 2–3 times and vigorously rolling the syringe between the palms for 30 seconds immediately prior to administration.

Decitabine is administered subcutaneously. Doses greater than 5 mL should be divided equally into 2 syringes and injected into 2 separate sites. Rotate sites for each injection (thigh, abdomen, or upper arm). New injections should be given at least 1 inch from an old site and never into areas where the site is tender, bruised, red, or hard

Drug Procurement:

Decitabine must be obtained from commercial sources. Cost of this agent will be subject's responsibility

8.2.1 Name of Agent: Venetoclax**Product description:**

Venetoclax is manufactured by AbbVie Inc. and is commercially available. It is supplied as tablets

Route of administration:

Oral

Drug Procurement:

Venetoclax must be obtained from commercial sources. Cost of this agent will be subject's responsibility

9.0 CORRELATIVE STUDIES**9.1 Methods**

Immuno-detection and quantitation: As part of standard of care, all patients on this trial will have a bone marrow biopsy at baseline (pre-treatment), then every three months and as clinically indicated. For each bone marrow sample, the paraffin block be stored at the pathology department for testing in formalin-fixed paraffin-embed embedded tissue. For quantitative analysis of DNMT1, paraffin blocks from different time-points will be cut onto the same slide for staining. The Pathology department will send 4 micron section slides to the Cleveland Clinic lab of [name] where immunostaining will be performed on bone marrow biopsy slides (4 μ m), positive and negative controls. Nuclei positive for the targeted

biomarker are identified and quantified in high resolution, large field-of-view images per ImageIQ algorithms (Image IQ Inc., Cleveland, OH) after subtraction of bone from the original image. DNMT1 quantification is correlated with bone marrow morphology parameters and hematologic response as previously described.⁴

Peripheral blood or Bone marrow aspirate collection: Peripheral blood or bone marrow aspirates for correlate analyses will be collected at three months intervals. When patients come in for routine blood draws or bone marrow aspirates done as part of their routine clinical care, an extra tubes with ~ 8 ml will be collected every three months. These samples will be cryopreserved for future analysis and stored at the Einstein lab of [name]. Blood or bone marrow will be collected in a one 8mL (purple or green top) tube at pre-treatment baseline and every three months if patient is having blood drawn or a Bone marrow biopsy done at Montefiore cancer center or any other site where the protocol is open. These samples will be used for flow cytometry analysis of DNMT1 protein levels in non-G0 cells if needed to confirm results of DNMT1-protein analyses in the bone marrow biopsies: Cryopreserved mononuclear cells from patient blood or marrow are thawed and fixed using formaldehyde (1%) and methanol (90%). Fixed cells are stained for DNMT1 and cell surface antigens. Cell cycle analysis is performed using DAPI staining. The expression of DNMT1 in white blood cells in S-phase is measured as mean fluorescent intensity (MFI) normalized to a control as previously described.²² Samples may also be used for preclinical research analyzing mechanisms of resistance to HMA and/or venetoclax treatment.

10.0 STUDY PARAMETERS AND CALENDAR

STUDY CALENDAR

Study Days:	Pre-study/Screening ¹	Induction Phase, Day 1 (+/- 4 days)	Long-term Treatment phase – 4-week treatment intervals – Day 1 (+/- 4 days)	End of Treatment ⁹
REQUIRED ASSESSMENTS				
Informed consent	X			
Demographics	X			
Medical History	X			
Height	X			
Weight	X	X		X
Vitals	X	X	X	X
Physical Examination	X	X	X	
Concomitant Medications	X	X		
Performance status	X	X		
Baseline Symptoms	X	X		
SAE and > grade 2 AE Assessment	X	X	X ²	X
CBC w/diff	X	X ³	X ³	X
CMP	X	X ⁴	X ⁴	X
LDH, uric acid	X	X ⁴		
Pregnancy test ¹⁰	X			
DISEASE ASSESSMENT				
Bone Marrow Biopsy or peripheral blood pathology		X ¹¹	X ⁵	X ⁶
TREATMENT				
Decitabine/venetoclax ⁷		X	X	
CORRELATIVE STUDIES (Refer to section 9 for details)				
Peripheral blood and/or Marrow Samples ⁸	X	X	X ⁵	X ⁶

¹Pre-study assessments for screening should be completed within 21 days of registration. All other assessments are ± 3 days unless otherwise noted. Pre-study/screening starts from when patient signs the consent.

²May be captured continuously

³During induction phase weeks 1-12, CBC needs to be checked a minimum of weekly. Study only *requires* CBC to be collected at start of each treatment interval to evaluate toxicity and hematologic response in the long-term phase and beyond; however, treating physicians should assess CBC as clinically indicated depending on disease status and need for potential transfusion support or other supportive care, as per their judgement and standard clinical practice. Any CBC results collected should be considered data for efficacy analysis. See section 6.2.

⁴During induction phase weeks 1-12, CMP, LDH, uric acid are *required* a minimum of every 3 weeks. During the long-term treatment phase, CMP, LDH, uric acid are only *required* at day 1 of treatment. Treating physicians should consider increased frequency as clinically indicated for supportive as per their judgement and standard clinical practice.

⁵Marrow should be obtained at the end of cycle 3 and every three months for the first two years. After two years BM biopsy every six months. Marrow timing may be considered ± 14 days. IHC will be completed from core biopsy samples processed in the department of pathology per standard of care.. Peripheral blood samples should be sent the same day as any marrow samples when able.

⁶If feasible but not mandated, but especially in cases where EOT is due to progressive disease.

⁷See Treatment Schema and section 6 for details.

⁸Correlative samples are not mandatory and are obtained when able

⁹End-of-treatment evaluations should be done when able but is not mandatory

¹⁰For women of childbearing age

¹¹Bone marrow biopsy done before enrolling in the study done within 28-days of study therapy is acceptable.

11.0 MEASUREMENT OF EFFECT

Responses for CR, PR and HI will be described per IWG criteria for MDS and MPN^{23,24}. For AML will use ELN response criteria. Additionally, in order to focus the most objective outcomes, additional MDS/MPN response criteria of spleen response and symptoms response will not be part of the measurement of effect of response, although will be collected as available for descriptive purposes.

Table 2: Criteria for Hematologic Improvement (HI)

Hematologic Improvement (HI)	Response Criteria (Must last at least 8 weeks)
Erythroid Response (pretreatment < 11g/dL)	
 • Hgb increase by \geq g/dL • Relevant reduction of units of RBC transfusions by an absolute number of at least 4 RBC transfusions/8 weeks compared with the pretreatment transfusion number in the previous 8 weeks.
Platelet response (pretreatment, < $100 \times 10^9/L$)	
 • Absolute increase of $\geq 30 \times 10^9/L$ for patients with $> 20 \times 10^9/L$ platelets • Increase from $< 20 \times 10^9/L$ to $> 20 \times 10^9/L$ and by at least 100%
Neutrophil response (pretreatment < $1.0 \times 10^9/L$)	
 • At least 100% increase and an absolute increase $> 0.5 \times 10^9/L$

*Pretreatment values should not be influenced by transfusion, if they are considered transfusion dependent

Table 3: Response criteria for patients with primary diagnosis of MDS²³

Category	Response Criteria (response must last at least 4 weeks)
Complete Remission	
 • Bone marrow: $\leq 5\%$ myeloblasts with normal maturation of all cell lines. (Note persistence of dysplasia) • Peripheral Blood 
 ◦ Hgb $\geq 11\text{g/dL}$ ◦ Platelets $\geq 100 \times 10^9/\text{L}$ ◦ Neutrophils $\geq 1.0 \times 10^9/\text{L}$ ◦ Blasts 0%
Partial Remission	
 • All CR criteria if abnormal before treatment except: 
 ◦ Bone marrow blasts decreased by $\geq 50\%$ over pretreatment but still $> 5\%$ ◦ Cellularity and morphology no relevant
Marrow CR	
 • Bone marrow: $\leq 5\%$ myeloblasts and decrease by $\geq 50\%$ over pretreatment • Peripheral blood: if HI responses, should be noted in addition to marrow CR. (for this protocol, marrow CR absent HI is NOT considered a response)
Stable Disease	
 • Failure to achieve at least PR, but no evidence of progression for > 8 weeks
Failure	
 • Death during treatment or disease progression characterized by worsening of cytopenias, increase in percentage of bone marrow blasts, or progression to a more advanced MDS subtype than pretreatment
Relapse after CR or PR	
 • At least one of the following: 
 ◦ Return to pretreatment bone marrow blast percentage ◦ Decrement of $\geq 50\%$ from maximum remission/response levels in granulocytes or platelets ◦ Reduction in Hgb concentration by $\geq 1.5\text{g/dL}$ or transfusion dependence
Cytogenetic response	
 • Complete: Disappearance of the chromosomal abnormality without appearance of the new ones • Partial: at least 50% reduction of the chromosomal abnormality
Disease Progression	
 • For patients with: 
 ◦ Less than 5% blasts: $\geq 50\%$ increase to $> 5\%$ blasts ◦ 5%-10% blasts: $\geq 50\%$ increase to $> 10\%$ blasts ◦ 10-20% blasts: $\geq 50\%$ increase to $> 20\%$ blasts • Any of the following: 
 ◦ At least 50% decrement from maximum remission/response in granulocytes or platelets

- Reduction in hgb by $\geq 2\text{g/dL}$
- Transfusion dependence

In general, all reductions in to define progression counts must not be attributable to treatment. If treatment causes transient reductions in counts, response should be considered durable through therapy. Other concomitant causes such as infection or bleeding need to be considered to ensure there is not concomitant causes.

Table 4: Response Criteria for patient with a primary diagnosis of MDS/MPN²⁴

Category	Response Criteria (response must last at least 4 weeks)
Complete Remission (presence of all of the following)	
 • Bone marrow: $\leq 5\%$ myeloblasts with normal maturation of all cell lines, and return to normal cellularity • Osteomyelofibrosis absent or equal to “mild reticulin fibrosis” (\leq grade 1 fibrosis) • Peripheral Blood 
 ◦ WBC $\leq 10 \times 10^9/L$ ◦ Hgb $\geq 11g/dL$ ◦ Platelets $\geq 100 \times 10^9/L; \leq 450 \times 10^9/L$ ◦ Neutrophils $\geq 1.0 \times 10^9/L$ ◦ Blasts 0% ◦ Neutrophil precursors reduced to $\leq 2\%$ ◦ Monocytes $\leq 1 \times 10^9/L$ • Extramedullary disease: complete resolution of extramedullary disease present before therapy (e.g. cutaneous disease, disease-related serous effusions) including palpable splenomegaly • Persistent low-level dysplasia is permitted given subjectivity of assignment of dysplasia
Complete cytogenetic remission	
 • Resolution of previously present chromosomal abnormality (known to be associated with MDS, MPN, or MDS/MPN) as seen on classic karyotyping with minimal of 20 metaphases or FISH
Partial Remission	
 • Normalization of peripheral counts and hepatosplenomegaly with bone marrow blasts (and blast equivalents) reduced by 50%, but remaining $> 5\%$ of cellularity, except in cases of MDS/MPN with \leq bone marrow blasts at baseline
Marrow response	
 • Optimal marrow response: presence of all marrow criteria for CR without normalization of peripheral blood indices as per CR • Partial marrow response: bone marrow blasts (and blast equivalents) reduced by 50%, but remaining $> 5\%$ of cellularity, or reduction in grading of reticulin fibrosis from baseline on at least 2 bone marrow evaluations spaced at least 2 months apart.
Stable Disease	
 • Failure to achieve at least PR, but no evidence of progression for > 8 weeks
Failure	
 • Death during treatment or disease progression characterized by worsening of cytopenias, increase in percentage of bone marrow blasts, or progression to a more advanced MDS subtype than pretreatment
Relapse after CR or PR	
 • At least one of the following: 
 ◦ Return to pretreatment bone marrow blast percentage ◦ Decrement of $\geq 50\%$ from maximum remission/response levels in granulocytes or platelets

	
 ○ Reduction in Hgb concentration by $\geq 1.5\text{g/dL}$ or transfusion dependence
Cytogenetic response	
 • Complete: Disappearance of the chromosomal abnormality without appearance of the new ones • Partial: at least 50% reduction of the chromosomal abnormality
Disease Progression: (Combination of 2 major criteria, 1 major and 2 minor criteria, or 3 minor criteria)	
 • Major Criteria: 
 ○ Increase in marrow blast count 
 ■ Less than 5% blasts: $\geq 50\%$ increase to $> 5\%$ blasts ■ 5%-10% blasts: $\geq 50\%$ increase to $> 10\%$ blasts ■ 10-20% blasts: $\geq 50\%$ increase to $> 20\%$ blasts ○ New extramedullary disease 
 ■ worsening splenomegaly ■ Extramedullary disease outside the spleen (new hepatomegaly) • Minor Criteria 
 ○ Transfusion dependence (at least 2 units of red blood cell transfusion in past month for hgb $< 8.5\text{g/dL}$ not associated with clinically overt bleeding nor secondary to therapy) ○ Significant loss of maximal response on cytopenias $\geq 50\%$ decrement from maximum remission/response in granulocytes or platelets ○ Reduction in Hgb by $\geq 1.5\text{g/dL}$ from best response or from baseline as noted on complete blood count

Table 5: Response Criteria for patient with AML

Category	Definition	Comment
Response		
CR without minimal residual disease (CRM _{RD})	
 • If studied pretreatment, CR with negativity for a genetic marker by RT-qPCR, or CR with negativity by MFC 	
 • Sensitivities vary by marker tested, and by method used; therefore, test used and sensitivity of the assay should be reported; analyses should be done in experienced laboratories (centralized diagnostics)
Complete remission (CR)	
 • Bone marrow blasts $<5\%$; absence of circulating blasts and blasts with Auer rods; absence of extramedullary disease; ANC $\geq 1.0 \times 10^9/\text{L}$ (1000/microL); platelet count $\geq 100 \times 10^9/\text{L}$ (100,000/microl) 	
 • MRD⁺ or unknown
CR with incomplete	
 • All CR criteria except for residual neutropenia ($<1.0 \times 10^9/\text{L}$) 	
 •

hematologic recovery (CR _i)	[1000/microL]) or thrombocytopenia (<100 × 10 ⁹ /L [100,000/microL])	
Morphologic leukemia-free state (MLFS)	• Bone marrow blasts <5%; absence of blasts with Auer rods; absence of extramedullary disease; no hematologic recovery required	Marrow should not merely be "aplastic"; at least 200 cells should be enumerated or cellularity should be at least 10%
Partial remission (PR)	• All hematologic criteria of CR; decrease of bone marrow blast percentage to 5 to 25%; and decrease of pretreatment bone marrow blast percentage by at least 50%	• Especially important in the context of phase 1/2 clinical trials

Treatment Failure

Primary-refractory disease	• No CR or CR _i after 2 courses of intensive induction treatment; excluding patients with death in aplasia or death due to indeterminate cause	• Regimens containing higher doses of cytarabine are generally considered as the best option for patients not responding to a first cycle of 7+3; the likelihood of responding to such regimens is lower after failure of a first
Death in aplasia	• Deaths occurring ≥7 days following completion of initial treatment while cytopenic; with an aplastic or hypoplastic bone marrow obtained within 7 days of death, without evidence of persistent leukemia	
Death from indeterminate cause	• Deaths occurring before completion of therapy, or <7 days following its completion; or deaths occurring ≥7 days following completion of initial therapy with no blasts in the blood, but no bone marrow examination available	

Response criteria for clinical trials only

Stable disease	• Absence of CR _{MRD} -, CR, CR _i , PR, MLFS; and criteria for PD not met	• Period of stable disease should last at least 3 months
Progressive disease (PD)*†	
Evidence for an increase in bone marrow blast percentage and/or increase of absolute blast counts in the blood:
 
 • >50% increase in marrow blasts over baseline (a minimum 15% point increase is required in cases with <30% blasts at baseline; or persistent marrow blast percentage of >70% over at least 3 months; without at least a 100% improvement in ANC to an absolute 	
Category mainly applies for older patient given low-intensity or single-agent "targeted therapies" in clinical trials
 
In general, at least 2 cycles of a novel agent should be administered
 
Some protocols may require blast increase in 2 consecutive marrow assessments at least 4 weeks apart; the date of progression should then be defined as of the first observation date

	
level ($>0.5 \times 10^9/L$ [500/microL], and/or platelet count to $>50 \times 10^9/L$ [50,000/microL] nontransfused); or
 
 • $>50\%$ increase in peripheral blasts (WBC \times % blasts) to $>25 \times 10^9/L$ ($>25,000/\text{microL}$) (in the absence of differentiation syndrome)[¶]; or • New extramedullary disease 	
Some protocols may allow transient addition of hydroxyurea to lower blast counts
 
"Progressive disease" is usually accompanied by a decline in ANC and platelets and increased transfusion requirement and decline in performance status or increase in symptoms

--	---	---

Relapse

Hematologic relapse (after CR _{MRD-} , CR, CR _i)	Bone marrow blasts $\geq 5\%$; or reappearance of blasts in the blood; or development of extramedullary disease	
Molecular relapse (after CR _{MRD-})	If studied pretreatment, reoccurrence of MRD as assessed by RT-qPCR or by MFC	Test applied, sensitivity of the assay, and cutoff values used must be reported; analyses should be done in experienced laboratories (centralized diagnostics)

CR: complete response; MRD: measurable residual disease (also known as minimal residual disease); ANC: absolute neutrophil count; MLFS: morphologic leukemia-free state; WBC: white blood cell; IDH: isocitrate dehydrogenase; RT-qPCR: real-time quantitative polymerase chain reaction; MFC: multiparameter flow cytometry.

* The authors acknowledge that this new provisional category is arbitrarily defined; the category aims at harmonizing the various definitions used in different clinical trials.

¶ Certain targeted therapies, for example, those inhibiting mutant IDH proteins, may cause a differentiation syndrome, that is, a transient increase in the percentage of bone marrow blasts and an absolute increase in blood blasts; in the setting of therapy with such compounds, an increase in blasts may not necessarily indicate PD.

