2.2 Secondary Objective(s)

1. Percentage of MDS participants with complete remission (CR) and complete remission with incomplete marrow recovery (CRi)
2. Percentage of AML participants with complete remission (CR) and complete remission with incomplete marrow recovery (CRi)
- 3.

This will be calculated based on current International Working Group (IWG) criteria. CR is defined as absolute neutrophil count $> 1000/\text{microliter (mCL)}$, platelets $> 100k/\text{mCL}$, red cell transfusion independence, and bone marrow with $< 5\%$ blasts. CRi is defined as bone marrow with less than 5% blasts, and absolute neutrophils of $\leq 10000/\text{mCL}$ or platelets $\leq 100k/\text{mCL}$

4. Event-free survival (EFS)

EFS will be defined as the number of days from randomization to the date of progressive disease, relapse from CR or CRi, treatment failure or death from any cause.

5. Complete remission or complete remission with partial hematologic recovery rate (CR+CRh)

A response of CRh is defined as Bone marrow with $< 5\%$ blasts, peripheral blood neutrophil count $> 0.5 * 10^3/\text{mCL}$ and peripheral blood platelet count $> 0.5 * 10^5/\text{mCL}$.

6. Post baseline transfusion independence rate

Transfusion Independence is defined as a period of 56 days with no transfusion between first dose of study drug and the last dose of study drug + 30 days. The rate of conversion for red blood cells (RBC) and platelets is defined as percentage of participants being post-baseline transfusion independent from baseline transfusion dependence.

7. Rate of Hospitalization

Defined as hospitalization for complication related to myeloid malignancy or treatment. Initial admission for diagnosis or initiation of therapy will not be considered an event.

8. Infection rate requiring hospitalization

Defined as being hospitalized due to an infection or sepsis.

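### The marrow criterion for relapse in MDS and MDS/MPN has no blast floor, so a patient who entered at or below 5% blasts can be counted as relapsed while still meeting CR

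*Combined protocol and SAP*

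**What the plan says.** - **Relapse.** In Table 3 (MDS) and Table 4 (MDS/MPN), one criterion is enough. The marrow criterion is "Return to pretreatment bone marrow blast percentage", with no absolute threshold. The others concern granulocytes, platelets, haemoglobin and transfusion dependence.
- **CR.** Table 3 asks for at most 5% "myeloblasts with normal maturation of all cell lines" plus blood criteria. Table 4 asks for at most 5% "myeloblasts with normal maturation of all cell lines, and return to normal cellularity" plus further criteria. Neither requires blasts to have fallen. Marrow CR in Table 3 does: its wording is "myeloblasts and decrease by" at least 50% over pretreatment.
- **Progression.** Both tables have a stratum headed "Less than 5% blasts", which needs a rise of at least 50% to a value above 5%.
- **Entry.** Section 4.1 admits MDS, CMML and MDS/MPN with no minimum blast percentage.
- **Use of relapse.** Section 2.2 lists among the EFS events "relapse from CR or CRi, treatment failure or death from any cause". Section 13.0 follows response duration for up to two years. Section 3.0 lets responders continue until relapse or progression, and Section 6.4 ends protocol monitoring at either.

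**The concern.** For a patient who enters at or below 5% blasts, the pretreatment percentage already lies inside the CR range. Going back to it is no evidence that remission has been lost, yet the relapse row counts it as an event. The progression row and the AML relapse row (Table 5, marrow blasts at or above 5%) both carry a floor, so the gap is confined to this criterion.

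Such events would shorten EFS and response duration, and by an amount that depends on the mix of baseline blast percentages. Because Section 6.4 stops protocol monitoring at relapse, later follow-up may not be there to correct a false event. The second rationale section numbered 1.4, on cohort expansion, intends the secondary-endpoint data to guide sample sizes for later trials, so the bias could be carried forward.

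**Working it through.** The plan gives no figure for this point, so there is none to reproduce. The check has three steps.

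**1. Do the rows conflict?** Let b be the pretreatment blast percentage and x an on-study value, both whole numbers (b = 1–20, x = 0–20), with blood counts in the CR range.

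- CR marrow criterion: x ≤ 5.
- Relapse marrow criterion: x back at or above b.
- Both hold when b ≤ x ≤ 5. For b = 1 to 5 this gives 5 + 4 + 3 + 2 + 1 = 15 pairs. For b above 5 there are none.
- With the strict under-5% limit in Section 2.2 (its CR text reads "red cell transfusion independence, and bone marrow with" under 5% blasts), there are 4 + 3 + 2 + 1 = 10 pairs, for b = 1 to 4.
- Progression from under 5% needs x ≥ 1.5b and x > 5, so it never overlaps CR.
- Adding x > 5 to the relapse criterion reduces the 15 pairs to 0.

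Worked path: 4% at entry, 2% at week 12 and 4% at week 24, with CR-range counts throughout. At week 24 the CR criteria are met. Progression is not, because 4% is not above 5%. The relapse criterion is met.

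**2. How often could counting error alone produce this path?** Assumptions:

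- True blasts at entry p are 2%, 3% or 4%.
- n cells are counted per marrow. n = 200 is borrowed from the AML comment on leukaemia-free state in Table 5, since the plan sets no count for MDS; n = 500 is the alternative.
- Four follow-up marrows in year 1 (study calendar, footnote 5: end of cycle 3, then every three months).
- Baseline X ~ Bin(n, p). Follow-ups Y_j ~ Bin(n, p) if blasts are stable, or Bin(n, p/2) if treatment halves them. Counts are independent and all at or below 5%.
- Event: some Y_i < X, followed by a later Y_j ≥ X. This is a fall, then a return.

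Results by simulation (400,000 draws per setting), as the range over p:

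| True blasts on treatment | Cells | By 4th marrow |
|---|---|---|
| Halved | 200 | 29–34% |
| Halved | 500 | 9–20% |
| Stable | 200 or 500 | 45–47% |

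**3. How many patients are exposed?** In Table 3, PR requires blasts still above 5%, so a low-blast MDS patient can reach the relapse row only through CR.

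- Expected MDS CRs (Section 13.0): 32 × 0.36 = 11.5.
- The low-blast share is not stated. At an assumed 10–50%: 11.5 × 0.10 = 1.2 to 11.5 × 0.50 = 5.8, or roughly 1–6 patients.
- Expected false events by the fourth marrow, if all four are taken and counts stay in the CR range:
  - blasts halved: 1.2 × 0.09 = 0.1 to 5.8 × 0.34 = 2.0;
  - blasts stable: 1.2 × 0.45 = 0.5 to 5.8 × 0.47 = 2.7.

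A few of the approximately 10 planned patients with CMML, MDS/MPN or similar diseases would add to this.

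**The case against.** The strongest objections concern the size of the problem and how far the wording can be pushed.

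- **Same-marrow reading.** A reader might infer that one marrow can be both CR and relapse, for instance with blasts at 3% throughout. The documents do not support this firmly. The row concerns relapse after a response, the word return implies an earlier fall, and both tables require a response to last at least four weeks. The point rests only on the fall-then-return path.
- **Larger probabilities.** If any follow-up count at or above baseline were a relapse, the chance would be about 57% with one marrow and 85% with four. That needs the no-fall reading and no effect of treatment on blasts, so it is not the right measure.
- **All 32 MDS patients as the base.** Taking 10–50% of 32 gives 3–16 patients, but the row applies only after a response. The expected CRs are the right base.
- **Patient mix.** Section 1.3.4 discusses high-risk MDS, so low-blast entrants may be few. Section 4.1 does not restrict entry to that group, however, and the progression rows provide for baselines under 5%.
- **Judgement.** The calculation ignores pathologist judgement and correlation between readings. That is fair, so the percentages are illustrative.
- **Existing safeguard.** The text after Table 3 protects responses from transient treatment-related falls in counts. It does not address marrow blasts.

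The size objections stand and are reflected in the figures. None of them removes the conflict between the rows.

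**Conclusion.** The conflict holds as a defect in the outcome definition. In Tables 3 and 4, a patient who enters at or below 5% blasts, falls, and returns to the entry value with CR-range counts is in CR, has not progressed, and is still an EFS event.

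The likely effect is small in number: roughly 1–6 exposed MDS patients and between 0.1 and 2.7 expected false events by the fourth marrow. This rests on the assumed low-blast share, pure counting error and independent marrows. Among about 11.5 expected MDS complete responders, two such events would still be noticeable.

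It would be wrong to conclude that the trial's main results are compromised. The primary endpoint concerns dose interruptions, the CR-rate precision targets do not use relapse, and AML has its own floor. EFS is a descriptive secondary endpoint with no test or target. The effect on response duration is less firm than that on EFS, because response duration is followed but is neither listed in Section 2.2 nor given a defined end.

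**What to change.** For the EFS and response-duration analyses, count the marrow criterion of relapse in Tables 3 and 4 only when blasts have returned to the pretreatment percentage **and** are above 5%. No marrow within the CR range of those tables can then count as relapse. For anyone who enters above 5%, the added condition is met automatically, so nothing changes for them.

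The cost is one sentence for each table, with no change to sample size, alpha or power. The downside is that a true early relapse in a low-blast patient is dated slightly later, at the marrow that crosses 5% or by a blood-count criterion.

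Two things need reconciling alongside it. Section 2.2 uses under 5% for CR while Tables 3 and 4 use at most 5%, so a reading of exactly 5% should be assigned consistently. Relapse also bounds continued treatment (Section 3.0) and ends protocol monitoring (Section 6.4), so the sponsor should reconcile the CR, relapse and progression rows with those sections. This change concerns the analysis definition only, and no treatment rule is proposed.

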6.4 Duration of Follow Up

The evaluation of the primary and secondary endpoints of ORR, CIR, and DOR are continuous. If in the judgement of patients and the treating clinical team, patients are benefiting from this therapy, the therapy will be continued even after measurement of the primary end-point at week 12 but monitoring will continue every 4 weeks or more often if clinically indicated. Patients will be considered off-protocol monitoring if they develop relapsed or progressive disease.

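### Table 3 counts transfusion dependence as MDS progression without a baseline reference, a definition, or a stated link to the blast criterion

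*Combined protocol and SAP*

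**What the plan says.** In section 11.0, Table 3, the Disease Progression row for MDS has two parts. The first sets blast-increase thresholds by baseline blast percentage. The second is headed "Any of the following" and has three items: "At least 50% decrement from maximum remission/response in granulocytes or platelets", a haemoglobin fall of 2 g/dL or more, and "transfusion dependence". No AND or OR joins the two parts.

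The paragraph after the table adds that "all reductions in to define progression counts must not be attributable to treatment", and asks that infection and bleeding be considered as other causes.

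Section 2.2 item 6 defines the conversion rate as the "percentage of participants being post-baseline transfusion independent from baseline transfusion dependence", with independence meaning 56 days without transfusion. Section 2.2 also makes progressive disease an EFS event. Section 6.4 says: "Patients will be considered off-protocol monitoring if they develop relapsed or progressive disease".

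For MDS/MPN, Table 4 gives a fuller item: "Transfusion dependence (at least 2 units of red blood cell transfusion in past month for hgb" below 8.5 g/dL, excluding overt bleeding and therapy effects. There it is one minor criterion among several.

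**The concern.** Two of the three items in the second part of the row measure change: a fall from best response and a fall in haemoglobin. The third is a state, and a patient can be in that state before the first dose. Progression is meant to mark worsening, so a state that can be present at entry does not belong in the list unless it is tied to baseline.

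EFS and the stable-disease rate for the MDS group are at stake. An assessor who applies the row as written and one who reads *new* into it will classify the same unchanged patient differently. Section 5.0 names three recruiting centres, and the expansion phase exists largely to collect secondary efficacy data. If the reading is settled only after outcomes are known, the choice itself can bias the result.

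**Working it through.** The plan states no figure on this point, so the check is textual, with one scale calculation.

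**1. Are baseline-dependent MDS patients in the trial?** Yes. Sections 4.1 and 4.2 do not exclude them. Section 2.2 item 6 needs them as its denominator, and the Table 2 footnote provides for them.

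**2. Does any text exempt dependence present at entry?** No. The paragraph after Table 3 deals with count reductions and with treatment, infection or bleeding as causes. Dependence from the disease itself, unchanged since before treatment, is none of these. Where the tables mean *new* they can say so: Table 4 does for extramedullary disease.

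**3. What follows under each reading of the row?** Take an MDS patient who is dependent at entry, with stable blasts and counts.

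| Reading | Blast part | Second part | Result |
|---|---|---|---|
| Either part suffices | not met | met through transfusion dependence | progressive disease |
| Both parts required | not met | already met at entry | not progression, but the second part adds nothing |

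On the second reading the rule is also uneven. A patient independent at entry needs a blast increase plus a count change or new dependence, while a dependent patient needs only the blast increase.

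**4. Does the item fit the response criteria?** Table 2 credits an erythroid response for a fall of at least 4 red-cell units per 8 weeks, without requiring independence. As an invented example, take a patient who goes from 12 to 6 units per 8 weeks:

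- The fall is 12 − 6 = 6 units, which is at least 4, so this is hematologic improvement.
- The remaining need is 6 / 2 = 3 units per 4 weeks. That reaches the 2-unit monthly level in Table 4, the only unit-based description of dependence in the tables (given haemoglobin below 8.5 g/dL).

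With a marrow CR, Table 3 counts this patient as a responder. On the either-part reading, the progression row of the same table calls the patient progressive.

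**5. Which outcomes use the row?** EFS does (section 2.2), as do Stable Disease, which requires no evidence of progression for more than 8 weeks (Table 3), and the end of protocol monitoring (section 6.4).

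**6. Scale.** Let *f* be the share of MDS patients dependent at entry. The documents do not give *f*, so it is an assumption. Section 13.0 plans 32 MDS patients. The number meeting the item at entry is 32 × *f*:

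- *f* = 25%: 32 × 0.25 = 8
- *f* = 50%: 32 × 0.50 = 16

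If the dependence had to be new, the number would be 0 for any *f*.

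**The case against.** The strongest reply is that the surrounding text points to change. The Failure row describes progression through worsening cytopenias, rising blasts or a more advanced subtype than before treatment. The neighbouring items are reductions, and section 6.4 speaks of patients who develop progression. Many assessors will therefore read *new* into the item. This stands as a reason to expect inconsistent classification rather than universal misclassification. It does not repair the row, because none of that text amends it.

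Three stronger readings are tempting, and the documents do not support them.

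- *Every dependent MDS patient progresses on day 1.* This holds only if either part of the row suffices and the item is applied literally. The row does not state the first, and the surrounding text pulls against the second.
- *The transfusion-conversion endpoint is lost.* The section 2.2 window runs from first dose to 30 days after last dose, so it follows dosing and not the monitoring label. Section 6.3 ties removal to progression that does not respond to dose adjustment or that occurs at the maximum dose level. Section 3.0 foresees at least 12 weeks of treatment absent clear evidence of progression. Loss of the endpoint is not shown.
- *Table 4 has the same defect.* There, dependence is one minor criterion, and progression needs two major, one major plus two minor, or three minor criteria. A dependent patient starts with one minor criterion met but cannot progress on it alone.

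Table 3 is attributed to a cited published standard. Whether the wording comes from there cannot be judged from these documents, and it would not remove the ambiguity here.

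**Conclusion.** The point holds as a defect in a secondary-endpoint definition. On the natural either-part reading, an unchanged, baseline-dependent MDS patient meets progressive disease. On the both-parts reading, the item carries no information for such patients. Both readings need repair.

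The size rests on the unknown *f*: 8 to 16 of 32 MDS patients at an assumed 25% to 50%, and only on the either-part reading applied literally. The primary endpoint (dose interruptions in weeks 1-12), the expansion sizing on CR-rate precision and the Bayesian toxicity rule do not use this row. The plan attaches no hypothesis or decision rule to EFS. The correction is worth making before EFS or response is adjudicated, but it does not threaten the trial's main conclusion.

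**What to change.** The change concerns endpoint classification only and leaves treatment rules alone.

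1. In the Table 3 Disease Progression row, state whether either part suffices or both are required.
2. Replace the bare item with: *new transfusion dependence: in a patient transfusion-independent at baseline, or after on-study independence was achieved, not due to treatment, bleeding or infection*.
3. Define dependence for Table 3 consistently with section 2.2 item 6. That item defines independence (56 days) but not dependence. The 8-week look-back in Table 2 is the same length (8 × 7 = 56 days) and is a natural window.
4. Record baseline red-cell and platelet transfusion status. Table 2's look-back covers red cells only, since its platelet criterion uses counts, so platelet transfusion history has to be added.
5. As a lesser consistency edit, add *new* to the Table 4 minor criterion.

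The cost is a wording change in two tables and one added baseline data field. The downside is fewer early progression events. In a patient dependent at entry who has not become independent on study, a rising transfusion need would not count through this item; the blast and count items remain.
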